7.4.1.1 Eliciting Adverse Event Information

A consistent methodology of non-directive questioning should be adopted for eliciting AE information at all subject evaluation time points. Examples of nondirective questions from the Investigator to the subject include the following:

- "How have you felt since your last clinic visit?"
- "Have you had any new or changed health problems since you were last here?"

7.4.2 Serious Adverse Events

An SAE experience or reaction is any untoward medical occurrence (whether considered to be related to the study treatment or not) that at any dose:

- Results in death
- Is life-threatening (the subject is at a risk of death at the time of the event; it does not refer to an event that hypothetically might have caused death if it were more severe)
- Requires subject hospitalization or prolongation of existing hospitalization
- Results in persistent or significant disability/incapacity
- Is a congenital abnormality/birth defect
- Other medically significant events, which do not meet any of the criteria above, but may jeopardize the subject and may require medical or surgical intervention to prevent 1 of the other serious outcomes listed in the definition above.
- Examples of such events are blood dyscrasias (e.g., neutropenia or anemia requiring blood transfusion, etc) or convulsions that do not result in hospitalization.
- Confirmed cases of active TB should be recorded and reported as SAEs.
- Potential hepatotoxicity events that fulfill any of the following criteria should be recorded and reported as SAEs:

- ALT >3× ULN and total bilirubin >2× ULN
- ALT >8× ULN at any time, regardless of total bilirubin or accompanying symptoms
- ALT >5× ULN for ≥2 weeks, regardless of total bilirubin or accompanying symptoms. The elevation should be continuous for ≥2 consecutive weeks. If the level decreases for some time within 2 weeks, subject permanent discontinuation is not mandated, but left under Investigator discretion. Resuming the IMP should be discussed on a case by case basis.
- ALT >3× ULN, accompanied by symptoms which, as determined by the Investigator, are the result of hepatic injury (e.g., fatigue, nausea, vomiting, right upper quadrant pain or tenderness, fever, rash, eosinophilia [>5%]).

Any AE that results in an unplanned hospitalization or prolonged hospitalization should be documented and reported as an SAE. The following hospitalization scenarios are examples of events not considered to be SAEs:

- Hospitalization for a pre-existing condition, provided that any of the following criteria are met:
 - Routine treatment or monitoring of the studied indication, not associated with any deterioration in condition or
 - Elective or preplanned treatment for a pre-existing condition that is unrelated to the indication under study and has not worsened since the start of study treatment.
- Treatment on an emergency outpatient basis for an event not fulfilling any of the definitions of an SAE given above and not resulting in hospital admission.
- Social reasons and respite care in the absence of any deterioration in the subject's general condition.

Any SAEs occurring after a subject has received the last dose of study treatment will be collected and reported to R-Pharm International's designee through the end of the Safety Follow-Up Period (i.e., for a period of 22 weeks after the last dose of study treatment), regardless of the Investigator's opinion of causality. The Investigator must also inform participating subjects of the need to inform the Investigator of any SAE that occurs within this period. Any SAE with a start date after the Safety Follow-Up Period is not required to be reported unless the Investigator thinks that the event may be related to either the study treatment, study treatment administration, or a protocol procedure.

All deaths that occur during the protocol-specified AE reporting period, regardless of relationship to the study treatment, must be recorded on the SAE page in the eCRF and

immediately reported to R-Pharm International or their's designee. This includes death attributed to progression of RA.

Death should be considered an outcome and not a distinct event. The event or condition that caused or contributed to the fatal outcome should be recorded as the description of event on the SAE page in the eCRF. Generally, only 1 such event leading to death should be reported.

The use of the term "**sudden death**" as the description of an event should be used, for example, in case of presence of such cardiovascular diagnosis in the source documents or occurrence of an unexpected cardiac death within scenarios as described in Potential MACE Reporting Site Manual. If the cause of death is unknown and cannot be ascertained at the time of reporting, "**unexplained death**" should be recorded on the SAE page as the description of the event in the eCRF. If the cause of death later becomes available (e.g., after autopsy), "unexplained death" should be replaced by the established cause of death.

7.4.2.1 Lack of Efficacy or Worsening of Rheumatoid Arthritis

Medical occurrences or symptoms of deterioration that are anticipated as part of RA should be recorded as an AE if judged by the Investigator to have unexpectedly worsened in severity or frequency or changed in nature at any time during the study. When recording an unanticipated worsening of RA on the AEs eCRF page, it is important to convey the concept that the condition has changed by including applicable descriptors (e.g., "accelerated RA"). Events that are clearly consistent with the expected pattern of progression of the underlying disease, as determined by the Investigator, should not be recorded as AEs; these data will be captured as efficacy assessment data only. Every effort should be made to document progression using objective criteria. If there is any uncertainty as to whether an event is an AE or due to disease progression, it should be reported as an AE.

Any worsening of RA that meets the criteria for seriousness should be reported as an SAE.

7.4.2.2 *Overdose*

Study treatment overdose is the accidental or intentional use of the drug in an amount higher than the dose being studied. An overdose or incorrect administration of study treatment is not an AE unless it results in untoward medical effects. Any study treatment overdose or incorrect administration of study treatment should be noted on the Study Drug Administration eCRF. All AEs associated with an overdose or incorrect administration of study treatment should be recorded on the AEs eCRF page.

7.4.2.3 Reporting and Follow-up Requirements for Pregnancies

Pregnancies in Female Subjects

A urine pregnancy test will be conducted on all females of childbearing potential as presented in the Schedule of Events (Table 1).

If a subject becomes pregnant after the administration of any study treatment, R-Pharm International and/or R-Pharm International's designee should be informed immediately. Study treatment should be discontinued as soon as the pregnancy is known, and the following should be completed:

- The subject should immediately discontinue further administration of study treatment.
- The subject should return for an EoT Visit.
- All scheduled safety assessments must be performed unless contraindicated by pregnancy (harmful to fetus) or the subject withdraws informed consent.

The Investigator must inform the subject of information currently known about potential risks and about available treatment alternatives. The pregnancy should be followed up to determine outcome including spontaneous or voluntary termination, details of the birth, and the presence or absence of any birth defects, congenital abnormalities, or maternal and/or newborn complications.

Full details will be recorded on a Pregnancy Report eCRF and submitted via the Electronic Data Capture (EDC) system, and reporting details will be detailed in the Study Manual. The Investigator will update the Pregnancy Report eCRF with additional information as soon as the outcome of the pregnancy is known.

If the outcome of the pregnancy is an SAE then this must be additionally reported as an SAE on the appropriate eCRF page.

Pregnancies in Female Partners of Male Subjects

Male subjects will be instructed through the ICF to immediately inform the Investigator if their partner becomes pregnant during the study and up to 3 months after the subject received the last injection of study treatment. A Pregnancy Report eCRF should be completed by the Investigator within 1 working day after learning of the pregnancy and submitted via the EDC system. Attempts should be made to collect and report details of the course and outcome of any pregnancy in the partner of a male subject exposed to the study treatment. The pregnant partner will need to sign an Authorization for Use and Disclosure of Pregnancy Health Information to allow for follow-up on her pregnancy. Once the authorization has been

signed, the Investigator will update the Pregnancy Report eCRF with additional information on the course and outcome of the pregnancy. An Investigator who is contacted by the male subject or his pregnant partner may provide information on the risks of the pregnancy and the possible effects on the fetus, to support an informed decision in cooperation with the treating physician and/or obstetrician.

7.4.3 Adverse Events of Special Interest

The following safety concerns were identified as AESIs based upon either the safety data available to date (refer to the most recent version of the Investigator's Brochure) for OKZ or drug class-related events for a biologic IL-6 inhibitor:

- Infections (particularly serious infections), including TB and opportunistic infections
- Confirmed cases of active TB must also be recorded as an SAE.
- Malignancies
- The Investigator will be asked to provide relevant medical information/documentation (e.g., pathology/histology reports) on all malignancy cases, whether considered serious or not, as these cases will be recorded in the safety database.
- Elevation of blood lipids (e.g., hypercholesterolemia, blood cholesterol increased, blood triglycerides increased, hypertriglyceridemia, and elevation of LDL)
- Systemic injection reactions and hypersensitivity reactions, including anaphylaxis
- Refer to Appendix 3 (Section 13.3) for details on diagnosing anaphylaxis.
- GI perforation
- CV events
- Neutropenia, thrombocytopenia, leukocytopenia, and pancytopenia
- Hepatotoxicity
- The Investigator will be asked to provide relevant medical information/documentation (e.g., laboratory test results, including tests for viral hepatitis and, if performed, liver biopsy) on all hepatotoxicity cases, whether considered serious or not, as these cases will be recorded in the safety database (see Section 7.4.3.4).
- Injection site reactions

- Demyelination in peripheral or central nervous system
- Autoimmune disorders.

All of the events listed above will be analyzed as AESIs; some of these events are further detailed below.

7.4.3.1 Infections

Frequency, duration, and severity of infectious complications along with those requiring treatment (e.g., antibiotic, antiviral, etc) will be monitored and evaluated. Investigators will also educate subjects, parents, and/or caregivers about the symptoms of infections and will provide instructions on dealing with these infections.

Physicians should exercise caution when considering the use of OKZ in subjects with a history of recurring infection or with underlying conditions (e.g., diabetes) that may predispose subjects to infections. Study Treatment should not be administered to subjects with active or clinically significant infection. Vigilance for timely detection of serious infection is recommended for subjects receiving biologic agents for treatment of RA, as signs and symptoms of acute inflammation may be lessened due to suppression of the acute phase reaction. Subjects must be instructed to contact their physician immediately when any symptom suggesting infection appears, in order to assure rapid evaluation and appropriate treatment. The Investigator may be asked to provide relevant medical information/documentation (e.g., result of bacterial examination or cultures).

Any infection that meets the criteria for seriousness should be reported as an SAE.

7.4.3.2 Systemic Injection Reactions, Including Anaphylaxis

A systemic injection reaction is any untoward medical hypersensitivity-like event, other than injection site reactions, occurring during or after study treatment administration that can be at least possibly attributed to the study treatment. Systemic injection reactions are further classified as acute and delayed based on timing and presentation of symptoms typical for hypersensitivity reactions.

Acute and delayed reactions to the study treatment should be reported according to the judgment of the Investigator, based on the typical clinical features.

Any systemic allergic reaction that meets the criteria for seriousness should be reported as an SAE.

Subjects will be observed for AEs at the study site for at least 2 hours after the first administration of study treatment (Visit 1 [OLE Baseline/Week 24]) and for at least 30

minutes after the second administration of study treatment (Visit 2 [Week 26] for subjects receiving OKZ 64 mg q2w and Visit 3 [Week 28] for subjects receiving OKZ 64 mg q4w). For injections administered by the subject (or caregiver, if applicable), subjects will record in the Subject Diary (see Section 5.5) any complaints, signs, or symptoms that occur during or after the injection. Subjects will be asked to contact the Investigator if any significant reactions occur within the 2 hours following study treatment injection.

Acute injection reactions are usually defined as at least 1 of the following signs or symptoms occurring during or within 2 hours of the study treatment injection:

- Hypotension
- Urticaria
- Flushing
- Facial or hand edema
- Throat tightness, oral cavity, or lip edema
- Headache
- Shortness of breath.

The Investigator should report any AE of acute systemic injection reaction as "anaphylaxis" if it meets the Clinical Criteria for Diagnosing Anaphylaxis, as specified in Appendix 3 (Section 13.3).

The study site must have adequate arrangements to manage anaphylactic reactions.

Delayed injection reactions are usually defined as at least 2 of the following 4 signs or symptoms occurring within 1 day to 14 days following the injection:

- Rash
- Fever (more than 100°F [38°C])
- Polyarthralgias
- Myalgias.

7.4.3.3 Gastrointestinal Perforation

Timely diagnosis and appropriate treatment may reduce the potential for complications of diverticulitis and thus reduce the risk of GI perforations. Therefore, subjects should be made aware of the symptoms potentially indicative of diverticular disease, and they should be

instructed to alert their healthcare provider as soon as possible if these symptoms arise. Permanent discontinuation of OKZ is required for subjects who develop diverticulitis and/or GI perforation.

Any GI perforation or diverticulitis that meets the criteria for seriousness should be reported as an SAE.

7.4.3.4 Hepatotoxicity

The Investigator will be asked to provide relevant medical information/documentation (e.g., laboratory test results) for all serious and non-serious cases of potential hepatotoxicity.

Potential hepatotoxicity is defined as laboratory results that fulfill any of the following criteria (in all cases, AST may be substituted for ALT if ALT results are not available):

- ALT $>3 \times$ to $\leq 5 \times$ ULN
- ALT $>5 \times$ ULN
- ALT >3× ULN and total bilirubin >2× ULN

Laboratory results that satisfy any of the criteria for potential hepatotoxicity should be followed by a repeat test within 72 hours, which must include total bilirubin, direct and indirect bilirubin, gamma-glutamyl transferase (GGT), INR, alkaline phosphatase, creatine phosphokinase, and hematology assessment. After that, testing should be repeated at least weekly and followed until resolution, stabilization, or return to baseline values. Additional testing may be limited to ALT, AST, alkaline phosphatase, and bilirubin if all other laboratory results are within normal limits. The number of LFTs included in each repeat testing may be further reduced to include only those parameters which remain abnormal (i.e., abnormalities that stabilize, resolve, or return to within baseline values do not require repeat testing).

Potential hepatotoxicity events that fulfill any of the following criteria must also be recorded as SAEs in the eCRF (in all cases, AST may be substituted for ALT if ALT results are not available):

- ALT >3× ULN and total bilirubin >2× ULN
- ALT >8× ULN at any time, regardless of total bilirubin or accompanying symptoms
- ALT >5× ULN for ≥2 weeks, regardless of total bilirubin or accompanying symptoms. The elevation should be continuous for ≥2 consecutive weeks. If the level decreases for some time within 2 weeks, subject permanent discontinuation is not mandated, but

left under Investigator discretion. Resuming the IMP should be discussed on a case by case basis.

• ALT >3× ULN, accompanied by symptoms which, as determined by the Investigator, are with the result of hepatic injury (e.g., fatigue, nausea, vomiting, right upper quadrant pain or tenderness, fever, rash, eosinophilia [>5%])

For SAEs of potential hepatotoxicity, the Investigator should contact the Medical Monitor for guidance, as additional tests are needed to investigate all potential causes of liver toxicity (e.g., alcohol use, hepatitis infection, biliary tract disease, and concomitant medications). Work-up includes, but is not limited to:

- Obtaining a more detailed history of symptoms and prior or concurrent diseases.
- Obtaining a history of concomitant drug use (including nonprescription medications and herbal/dietary supplement preparations), alcohol use, recreational drug use, and special diets.
- Ruling out acute viral hepatitis (types A, B, C, D, and E), cytomegalovirus, Epstein-Barr virus, autoimmune or alcoholic hepatitis, nonalcoholic steatohepatitis, hypoxic/ischemic hepatopathy, and biliary tract disease.
- Obtaining a history of exposure to environmental chemical agents.
- Obtaining additional tests to evaluate liver function, as appropriate (e.g., INR, direct bilirubin, biliary tract ultrasonography/imaging results, liver biopsy).
- Considering gastroenterology or hepatology consultations.

All additional investigations should be recorded in the eCRF via the EDC system, and all records should be kept as source documents at the study site.

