6.11.1 Temporary Discontinuation of Study Treatment

Temporary discontinuation of study treatment is required for the situations described below. The Investigator should contact the Medical Monitor for guidance regarding restarting study treatment.

Study treatment will be held/interrupted if:

- Results from the repeat laboratory testing are not available at the time of the next scheduled dose
- ALT and/or AST remains >3× ULN with total bilirubin ≤2× ULN after repeat laboratory testing.
- Subjects have an active or clinically significant infection.
- Subject has a suspected malignancy (with the exception of local and resected basal or squamous cell carcinoma of the skin), after confirmation with the Medical Monitor.

Temporary interruption of study treatment should also be considered if, at the discretion of the Investigator, it is necessary for safety reasons (e.g., negative trends during laboratory monitoring or remaining abnormalities after retesting which do not require premature discontinuation of the study treatment but could be harmful for the patient according to the Investigator's judgement [Section 7.4.6.2], or other clinically significant newly diagnosed co-morbidity that requires additional assessments for clarification of the diagnosis, and the severity of which could worsen if study treatment is continued).

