6.11.2 Permanent Discontinuation of Study Treatment

The criteria for enrollment are to be followed explicitly.

If a subject who does not meet enrollment criteria is inadvertently enrolled, R-Pharm International or R-Pharm International's designee must be informed immediately, and the subject may be discontinued from study treatment.

If, in the opinion of the Investigator, a subject is consistently noncompliant with the protocol in regards to study procedures, use of concomitant medications, or dosing with the study treatment, R-Pharm International or R-Pharm International's designee must be informed as soon as it can be possible, and the case will be reviewed by R-Pharm International on a case-by-case basis and the noncompliant subject can be discontinued from the study treatment.

If the Investigator judges that the subject's health is deteriorating or not improving, the Investigator can elect to discontinue the subject from the study treatment. Appropriate standard of care, at the discretion of the Investigator, will be initiated.

In addition to the above, study treatment will be discontinued in the following circumstances:

• Investigator decides that the subject should be discontinued from the study treatment. If this decision is made because of an intolerable AE or a clinically significant

laboratory value, the study treatment is to be discontinued, appropriate measures are to be taken, and R-Pharm International or R-Pharm International's designee is to be notified.

- Subject is unwilling to continue the study treatment. If the subject discontinues from the study treatment, the Investigator should inquire about the reason for discontinuing.
- Subject presents with any of the following elevated LFTs (see also Appendix 1 [Section 13.1]):
- ALT or AST elevations >8× ULN at any time, regardless of total bilirubin or accompanying symptoms
- ALT or AST >5× ULN for ≥2 weeks regardless of total bilirubin or accompanying symptoms. The elevation should be continuous for ≥2 consecutive weeks. If the level decreases for some time within 2 weeks, subject permanent discontinuation is not mandated, but left under Investigator discretion. Resuming the IMP should be discussed on a case by case basis.
- ALT or AST elevations >3× ULN and total bilirubin value >2× ULN at any time

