- AST or ALT elevations >3× ULN accompanied by symptoms which, as determined by the Investigator, are the result of hepatic injury (e.g., fatigue, nausea, vomiting, right upper quadrant pain or tenderness, fever, rash, eosinophilia [>5%])
- Subject presents with any of the following laboratory abnormalities:
- Absolute neutrophil count <500×10⁶/L (<500/mm³)
- Two sequential lymphocyte counts <500×10⁶/L (<500/mm³)
- Platelet count $<50\times10^9/L$ ($<50,000/mm^3$ or $<50,000\times10^6/L$)
- Two sequential hemoglobin values ≤8.0 g/dL and decreased ≥20 g/L (2 g/dL) below OLE Baseline
- Creatinine value >2× ULN
- Subject has confirmation of a pregnancy during the study, as evidenced by a positive pregnancy test.
- R-Pharm International, a regulatory agency, or an ethical committee stops the study for any reason.
- Subject has a GI perforation.

- Subject diagnosed with diverticulitis
- Subject has a confirmed active TB.
- Subject has a positive IGRA result or repeated indeterminate IGRA results during the study, unless active TB is ruled out and the Medical Monitor confirms that study treatment can be resumed as described below:
- Subjects may resume the administration of study treatment if active TB is ruled out by a certified TB specialist or pulmonologist who is familiar with treating TB (as acceptable per local practice). The subject must also start prophylactic LTBI therapy according to country-specific/CDC guidelines (see Appendix 4 [Section 13.4]) and agree to complete the entire course of recommended LTBI therapy. Study treatment should not be administered until active TB is ruled out and the subject starts LTBI therapy.
- Subject has a severe or life-threatening infection that requires hospitalization.
- Subject has a malignancy (with the exception of local and resected basal or squamous cell carcinoma of the skin), after confirmation with the Medical Monitor.

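### A permanent stop for a liver rise in AST alone does not by rule become a hepatotoxicity SAE, because the stop criteria accept ALT or AST and the matching SAE criteria rest on ALT

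*Combined protocol and SAP*

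**What the plan says.** **Stop rule.** Section 6.11.2 ends study treatment permanently at four liver limits, each written for either enzyme. Three read: "ALT or AST elevations >8× ULN at any time, regardless of total bilirubin or accompanying symptoms"; "ALT or AST elevations >3× ULN and total bilirubin value >2× ULN at any time"; and "AST or ALT elevations >3× ULN accompanied by symptoms which, as determined by the Investigator, are the result of hepatic injury". The fourth is ALT or AST above 5 times ULN for at least 2 weeks. Appendix 1, the temporary hold in 6.11.1 and the mandatory retest in 7.4.6.2 also act on either enzyme.

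**SAE rule.** Section 7.4.2 lists the same four limits as SAEs but names ALT only, for example "ALT >8× ULN at any time, regardless of total bilirubin or accompanying symptoms". Section 7.4.3.4 repeats the four SAE criteria and defines potential hepatotoxicity. In both lists it adds the condition "AST may be substituted for ALT if ALT results are not available".

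**What SAE status brings.** Section 7.4.5.2 requires an SAE report within 24 hours of awareness. Section 7.4.3.4 requires Medical Monitor contact and a search for causes (viral, autoimmune, alcoholic, biliary, drug-related and others) for SAEs of potential hepatotoxicity. Section 11.6.1 repeats the contact for potential hepatotoxicity events that meet a seriousness criterion.

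**Availability.** ALT and AST are both in the chemistry panel (7.4.6.1), which is drawn at every visit (Table 1).

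**The concern.** A stop rule need not equal an SAE rule. Here, however, the plan chose to make these exact limits SAEs, and it accepts AST as sufficient when ALT is missing. It gives no reason for ignoring AST when ALT is present. The SAE criterion for the 5-times limit, in both 7.4.2 and 7.4.3.4, even carries over a sentence about when permanent discontinuation is mandated. That sentence belongs to the stop rule and suggests, though it does not prove, that the lists were meant to match.

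At stake are the automatic SAE label and the mandated search for a cause in subjects whose liver tests were bad enough to end treatment. Long-term safety is the primary objective, hepatotoxicity is an AESI, and subjects take background MTX. In the Phase II study RA0056, raised AST was among the events reaching at least 10% in an olokizumab group, and the only olokizumab SAE judged related was an abnormal liver function test (2.2.3.2). Those findings show relevance. They do not give the frequency of AST-only rises.

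**Working it through.** The plan gives no figure to reproduce. The check applies the rules of 6.11.2, 7.4.2 and 7.4.3.4 to illustrative cases.

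An AST-only stop means that AST meets a stop limit and ALT meets none of the four. PH is potential hepatotoxicity as 7.4.3.4 defines it. In ALT terms, that requires ALT above 3 times ULN in every branch.

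**ALT reported** (values in multiples of ULN)

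| Case | ALT | AST | Bilirubin | Other | Stop | SAE, 7.4.2 | SAE, 7.4.3.4 | PH |
|---|---|---|---|---|---|---|---|---|
| A | 4 | 9 | 1 | – | yes | no | no | yes |
| B | 2 | 9 | 1 | – | yes | no | no | no |
| C | 4 | 6 | 1 | 2 weeks | yes | no | no | yes |
| D | 2 | 6 | 1 | 2 weeks | yes | no | no | no |
| E | 2.5 | 4 | 2.5 | – | yes | no | no | no |
| F | 2.5 | 4 | 1 | hepatic symptoms | yes | no | no | no |

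- An AST-only stop meets neither SAE list in 4 of 4 limbs.
- In the bilirubin and symptom limbs (E, F), AST-only implies ALT at or below 3 times ULN. The case is therefore always outside PH. In the other two limbs it is outside PH only if ALT is at or below 3 times ULN (B, D against A, C).

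**ALT missing**

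| Case | AST | Bilirubin | Other | Stop | 7.4.2 | SAE, 7.4.3.4 |
|---|---|---|---|---|---|---|
| G | 9 | 1 | – | yes | silent on AST | yes |
| H | 6 | 1 | 2 weeks | yes | silent on AST | yes |
| I | 4 | 2.5 | – | yes | silent on AST | yes |
| J | 4 | 1 | hepatic symptoms | yes | silent on AST | yes |

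Section 7.4.2 applies its criteria to potential hepatotoxicity events, a term that only 7.4.3.4 defines and to which 7.4.3.4 attaches the AST substitution. A site that follows both sections would report G to J.

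**After the change.** With ALT or AST in both sections, all ten cases meet an SAE criterion.

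**Timing.** The SAE report is due within 24 hours of awareness. The retest, which includes creatine phosphokinase, is due within 72 hours of receiving the result (7.4.6.2). If awareness and receipt coincide, the report can fall due up to 72 − 24 = 48 hours before creatine phosphokinase is due. This applies to the three limbs that a single result can trigger. The 2-week limb needs repeat testing anyway.

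**The case against.** The strongest case is that this is a coherent design choice. Some AST rises are not hepatic, and the retest panel includes creatine phosphokinase. Stopping cautiously on either enzyme while basing the automatic label on ALT can be defended. The existing cover is also substantial:

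- The subject is stopped and retested within 72 hours and then at least weekly, with MTX held (7.4.6.2, Appendix 1). The retest already includes INR and fractionated bilirubin.
- The synopsis asks for documentation, including viral hepatitis tests, on all hepatotoxicity cases whether serious or not, with no cross-reference to 7.4.3.4. The same request in 7.4.3 does refer to 7.4.3.4 and so inherits its ALT basis.
- Every AE is assessed for seriousness (7.4.1), and 7.4.2 allows an SAE on medical judgement. In the symptom limb the investigator has already attributed the symptoms to hepatic injury.
- Where the investigator decides to stop for a clinically significant laboratory value, "appropriate measures are to be taken, and R-Pharm International or R-Pharm International's designee is to be notified" (6.11.2).
- A hold applies if "ALT and/or AST remains >3× ULN with total bilirubin ≤2× ULN after repeat laboratory testing", and 6.11.1 adds: "The Investigator should contact the Medical Monitor for guidance regarding restarting study treatment". That contact concerns restarting rather than cause, and the bilirubin limb falls outside it.
- The sponsor's designee and the DSMB review laboratory data (7.4.8, 7.4.4.1), and AST is tabulated by elevation threshold (9.4.6.2).

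All of this stands and keeps the point small. None of it supplies the automatic SAE label or the mandated cause work-up.

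A reader might infer that 7.4.2 and 7.4.3.4 contradict each other when ALT is missing. They do not: 7.4.2 omits the substitution but does not deny it, so this is a drafting gap that will rarely matter. A reader might also infer that these subjects are left unprotected, or that reported safety rates are materially wrong. The list above answers the first. For the second, the documents give no frequency from which any effect could be sized.

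**Conclusion.** The mismatch is real and minor. With both enzymes reported, an AST-only permanent stop triggers neither the 24-hour hepatotoxicity SAE report nor the cause work-up and Medical Monitor contact by rule, in 4 of 4 limbs. It matters most in the bilirubin and symptom limbs. There a second liver test is abnormal, or the investigator has judged that there is hepatic injury, yet the case is also outside potential hepatotoxicity as defined.

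The counts are of rule limbs, not subjects. The conclusion assumes that ALT is normally available and that the availability condition is read literally. All analyses are descriptive, so no test is affected, and no effect on AESI counts or on any estimate is claimed.

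**What to change.** In 7.4.2 and 7.4.3.4, write *ALT or AST* in every hepatotoxicity SAE criterion, and do the same in the definition of potential hepatotoxicity on which those criteria depend. Delete the two conditions in 7.4.3.4 that limit AST to cases without ALT. Leave the thresholds unchanged. The hold, retest, stop, Appendix 1 and SAE rules then use the same analytes, and the two SAE lists agree. If ALT was preferred on purpose, the lesser remedy is to say why AST-only stops are not automatic SAEs and to copy the substitution into 7.4.2.

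The cost is protocol wording in two sections plus an unknown number of extra SAE reports and work-ups, some for non-hepatic AST rises. Some reports will precede creatine phosphokinase and need correction at follow-up. Any AST above 3 times ULN with ALT at or below 3 times would also become potential hepatotoxicity and call for documentation, even without a stop.

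One analysis precaution is needed. Section 9.4.6.1.1 pools core and OLE data for SAE rates per 100 subject-years. Placebo and adalimumab time comes only from the core studies, while olokizumab time includes the OLE. If the core protocols use an ALT-based rule (an assumption, since they are not available here), widening the rule in the OLE alone could raise the olokizumab rates relative to those comparators. Flag SAEs that qualify on AST alone, and also show the pooled rates without them.
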